### **Specific Aim 3 (Comparative Effectiveness-Behavior and Action)**

To compare the effectiveness of these interventions on behavior or action, we will monitor early hospital arrival and EMS use for stroke over a 60-month period at the 2 intervention hospitals using an interrupted time-series analysis. Early hospital arrival will be defined as the proportion of stroke patients arriving within 3 hours from symptom onset while EMS utilization (%) will be defined as the proportion of stroke patients arriving to the emergency department by EMS. Segmented regression analysis will be conducted to estimate whether and how much the intervention changes EMS utilization in each of the 2 target hospitals and in aggregate at both hospitals. Autoregressive error will account for correlations of the data across time points. In secondary analyses, temporal trends in early hospital arrival and EMS utilization from 2 pre-selected non-intervention Chicago hospitals (St. Elizabeth and Swedish Covenant) and from hospitals in St. Louis, a comparable Midwestern city, will be compared with the 2 intervention neighborhoods/hospitals in Chicago.

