## 6. Statistical Analysis

**Statistical Considerations and Power:** Existing data of monthly onset-to-hospital arrival times and EMS utilization from January 2013 to December 2017 (five years; n=60 months) will be obtained through AHA. We will assume approximately one-third (20 months) will be post-intervention periods. The effect size will be defined as the sum of expected slope change (i.e. monthly change) over the standard deviation. Table 1 shows the study power by autocorrelation level and effect size. Assuming pre-intervention EMS use rate is 50% on average (SD: 3%; 40 months of data) and post-intervention EMS use rate is 55% on average (SD: 3%; 20 months of data; auto-correlation=0.3) and no trend change (“flat”) in pre- or post-intervention periods, this 5% step-increase will be significant at 90% power at a significance level of 0.05. For a 10% step-increase (the goal) with the same assumptions, power is nearly 100%.

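### The autoregressive segmented regression names no order, estimator or reference distribution, and at 60 months the common fits do not hold the 5% level (about 8.5-10.5% in a level-and-slope model)

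*Combined protocol and SAP*

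**What the plan says.** In section 4, under Specific Aim 3 (Comparative Effectiveness-Behavior and Action), the plan says "we will monitor early hospital arrival and EMS use for stroke over a 60-month period at the 2 intervention hospitals". The method is given as "Segmented regression analysis will be conducted to estimate whether and how much the intervention changes EMS utilization", at each hospital and for the two combined. The only statement on serial dependence is "Autoregressive error will account for correlations of the data across time points".

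Section 6, Statistical Analysis, gives the design inputs. On the split of the series: "We will assume approximately one-third (20 months) will be post-intervention periods". The earlier period is taken as 40 months with a mean of 50% and an SD of 3 points. The later period is described as "post-intervention EMS use rate is 55% on average (SD: 3%; 20 months of data; auto-correlation=0.3". The claim is that "this 5% step-increase will be significant at 90% power at a significance level of 0.05".

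No section lists the regression terms, the autoregressive order, the estimator, a degrees-of-freedom rule or a check of the realised type I error.

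**The concern.** An autoregressive error term protects the test only as far as the autocorrelation is estimated well. Fitting a level, a trend, a level change and a slope change to 60 points removes some of the slow movement that carries the autocorrelation, so the residuals look more independent than the errors are. Yule-Walker and maximum likelihood (ML) make no allowance for this; REML largely does. If the autocorrelation is underestimated, the standard errors of the level and slope changes are too small. Chance steps are then declared significant too often, and the intervals are too narrow.

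This affects each single test and interval in Aim 3, however many series are tested. Leaving the estimator open also allows it to be chosen after the data are seen, among fits whose error rates differ.

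**Working it through.** **Inputs from the documents.** 60 months, split 40/20; SD 3 points; autocorrelation 0.3; significance level 0.05; 5-point step; 413 + 353 = 766 stroke admissions in 2013 at the two intervention hospitals (section 5 table).

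**Assumptions.** AR(1) Gaussian errors; two-sided test; abrupt change at month 41. The main model has four terms: intercept, trend, level change and slope change. The plan does not list these, but section 6 defines effect size through a slope change, so a slope-change term is plausible.

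**Step 1: the plan's own figure.** With known correlation, Var(b) = σ²(X′V⁻¹X)⁻¹, where V has entries 0.3^|i−j| and σ = 3. Two-sided power for the 5-point step, with the correlation known or estimated:

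- step only: about 99.5%
- step plus trend: 77-83%
- four terms: 69-77%

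None of these is the stated 90%. The nearest variant was a one-sided ML z test with step plus trend, at 88.8%. The 10-point step gives above 99.5%, which agrees with the plan. The model behind the 90% is not stated and Table 1 is not in the available text, so the figure is not reproduced. That does not show it to be wrong, and the point below does not depend on it.

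**Step 2: bias in the estimated autocorrelation.** Simulated series with true value 0.3 and four terms. Mean estimates: Yule-Walker 0.19-0.20, ML 0.20, REML 0.29.

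**Step 3: effect on the standard error.** Putting 0.3 and then 0.2 into the formula in Step 1, the standard error of the level change is 2.01 and 1.88 points. The ratio is 1.88/2.01 = 0.94. On its own this turns a 5% z test into 2 × [1 − Φ(1.96 × 0.94)] = 2 × [1 − Φ(1.84)], or about 6.6%. The rest of the excess in Step 4 comes from sampling variation in the estimated correlation and from a residual variance that is also too low.

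**Step 4: rejection under no effect, nominal 5%, two-sided.** Four terms, correlation 0.3. Ranges are over separate simulation runs, mostly of 20,000 series.

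| Fit | Level change | Slope change |
|---|---|---|
| Yule-Walker/Prais-Winsten, t | 8.5-9.1% | 8.8-9.0% |
| ML, t | 8.5-8.9% | 8.8% |
| ML, z | 10.0-10.7% | 10.4-10.7% |
| REML, t | 6.4-7.0% | 6.0-6.4% |
| REML, reduced df | 5.9% | not run |
| Correlation known, t | 4.8-5.5% | 5.0-5.1% |

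Charging one further degree of freedom for the correlation brings the t-based Yule-Walker and ML figures to 8.1-8.3%. Coverage is 100% minus the rejection rate: for 8.5-10.5%, it is 91.5-89.5%.

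**Step 5: sensitivity, Yule-Walker and ML fits.**

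- Step only, correlation 0.3: about 7-8.5%.
- Step plus trend, correlation 0.3: about 7.5-9.5%.
- Four terms, correlation 0: about 6.5-8.5%.
- Four terms, correlation 0.5: about 9.5-13% (REML with t 7.4%; with reduced df 5.9%).
- Binomial counts: 766/12 ≈ 64 patients a month, so sampling SD at 50% is √(0.25/63.8) = 6.3 points. With autoregressive drift added: 7.4-7.8% for t-based fits, 9.3-9.4% for ML with z, and 6.2% for REML.

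**The case against.** The plan names neither Yule-Walker nor ML. REML fits the plan's sentence equally well, and with a t reference it gives about 6.5%. A reader might infer that the planned test has a type I error of 9-10%. The documents do not support that: the figure belongs to particular fits of a four-term model at a correlation of 0.3, and only ML with a z reference exceeds 10% there. This part of the objection stands, and the point is worded accordingly.

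The 0.3 is a planning value, not an observed one. If the true drift has SD 3 points and correlation 0.3 (an assumption), binomial noise dilutes the observed lag-1 correlation to 0.3 × 9/(9 + 39.2) ≈ 0.06 for the two hospitals combined. The excess for t-based fits is then nearer 2 to 3 points than a doubling. This stands as a limit on size, but the excess does not vanish: none of the Yule-Walker or ML settings run came down to 5%, including those with no autocorrelation.

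The plan also compares trends with control hospitals in secondary analyses, so a chance step would not be read alone. That helps interpretation but does not correct the standard errors.

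A reader might also suspect that the autoregressive term could be dropped after a preliminary test. No section mentions such a test, so this is not part of the concern.

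**Conclusion.** The concern holds in a conditional form. The plan relies on the autoregressive term for valid inference but leaves open the choices that decide whether it delivers it. At the plan's inputs, with a level-and-slope model, the common Yule-Walker/Prais-Winsten and ML fits put the autocorrelation at about 0.20 instead of 0.30 and reject about 8.5-10.5% of the time at a nominal 5%, with coverage of about 89.5-91.5%. With fewer terms, or with counts of about 64 a month, rejection is about 7-9.5%; it is higher if the autocorrelation is stronger.

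These sizes rest on AR(1) errors, a two-sided test, an abrupt change at month 41 and, for the main figure, the assumed four-term model. They should not be read as evidence that the 90% power claim is wrong, or as the error rate of an analysis already fixed in the plan. The weakness is moderate in size and cheap to remove.

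**What to change.** In section 4, Specific Aim 3 (Behavior and Action), list the regression terms and state three things:

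- The AR(1) segmented model is fitted by REML.
- Level and slope changes are tested against a t distribution, with degrees of freedom reduced for the estimated correlation (Satterthwaite or Kenward-Roger type) where the software offers it.
- The simulated type I error at 60 months is reported alongside the results.

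This brings the size to about 6-6.5% at a correlation of 0.3, which is close to the nominal level but not equal to it. The simulated figure lets readers see what remains. In section 6, recompute the power with the same model and method.

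The cost is a few sentences and a software option; no further data are needed. Intervals widen by roughly 10%. Simulated power for the 5-point step in the four-term model falls from about 75% (Yule-Walker) to about 69% (REML). Part of that fall is only the removal of excess false positives: with the correlation known, power is also about 68%.

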### **Specific Aim 3 (Comparative Effectiveness-Knowledge and Attitudes)**

In addition to assessing change in action, we will conduct a survey to assess changes in knowledge, self-efficacy, and barriers to calling 911 (i.e. mechanisms for behavioral change), we will use a 2 group pre/post test design among 198 community dwelling persons from the 2 intervention

neighborhoods compared to 198 from the 2 control neighborhoods. Participants will be recruited using Participant Interest Forms completed at Promoter-led events or at already occurring stroke informational events conducted several times per year at the 2 control PSCs. Incentives (\$25) will be provided to motivate individuals to participate. Control subjects will receive standard print materials regarding stroke risk factors, warning signs, and use of 911 (i.e. FAST materials). The 2 groups will be assessed at baseline and 1 year by phone interview in English or Spanish. The interviews will last approximately 30 minutes by telephone, and will not be audio recorded. Their responses will be written down in a password protected database.

*Consent and evaluation tools will be submitted as an amendment to the protocol at the start of year 2 after modifications are made based on the results of Aim 1.*

### **Sources of Data Collection Aim 1 (Focus Groups)**

**Research Material:** The data that results from the focus group is in the form of transcripts. During analysis, quotes from the participants will be organized into a coding document. Participants will also fill out a brief demographic form prior to participation.

**Access to Research Materials:** Access to research materials will be limited to IRB-approved personnel. All transcripts will be kept on NU's secured internal server, with folder-level access restricted to only those on the IRB list of approved personnel. Transcripts and demographic forms will be de-identified, and participants will be referred to by a study ID only. Original transcripts with identifiers will be destroyed once de-identified versions have been created. Personal identifiers will be kept only during recruitment, and destroyed when focus groups are complete. Any paper data will be kept in locked file cabinets at the Northwestern University, accessible only to the PIs and Study Coordinator.

### **Sources of Data Collection for Aim 2 (Implementation)**

**Research Material:** The data from the activity forms (participant and stroke promoter) will be collected by study personnel and transcribed into a database using REDCap for analysis and storage, an NIH-supported research data collection tool, which will be housed within NU's server and firewall.

**Access to Research Materials:** Access to research materials will be limited to IRB-approved personnel. All data will be stored in NU servers, available only to those with a password and login. Stored data will not contain human subject identifiers, except for Stroke Promoter ID number assigned by the Study Coordinator. Any paper evaluation forms will be kept in locked file cabinets within NU's Department of Neurology offices.

### **Sources of Data Collected for Aim 3 (Comparative Effectiveness-Behavior and Action)**

**Research Material:** Hospital data will be collected using the AHA-partnered Get With The Guidelines Stroke registry, a voluntary quality improvement registry into which participating hospitals use a web-based Patient Management Tool (Quintiles Inc., Cambridge, MA) to collect stroke-specific demographic, clinical, and hospital outcome data, access decision support, and provide real-time online reporting of performance on quality of care measures. Records are de-identified and collected for quality improvement with a waiver of informed consent under the common rule. All PSCs in Chicago and in St. Louis currently use this registry for data collection.

**Access to Research Materials:** Access to de-identified data will be limited to IRB-approved personnel.

#### **Sources of Data Collected for Aim 3 (Comparative Effectiveness-Knowledge and Attitudes)**

**Research Material:** Data from this aim will be collected using an interview format and conducted by the CEERIAS Study Coordinator by phone. These will be entered directly into a data collection tool on REDCap and housed on a password-protected storage space in the NU server and within its firewalls. Follow-up interviews at 1 year will be completed by phone and entered into the same server space.

**Access to Research Materials:** Access to research materials will be limited to IRB-approved personnel. All data will be stored in NU servers, available only to those with a password and login. Survey data will contain only a subject ID, assigned by the Study Coordinator.

### **6. Recruitment and Informed Consent**

#### **Focus Groups (Aim 1)**

Potential layperson and patient/caregiver focus group participants will be identified by community organizations we have partnered with and local hospitals (Holy Cross and Trinity Hospitals). Potential participants will be asked if a study researcher may contact them regarding a survey about stroke symptom recognition and action. At the time of recruitment, all procedures, risks and benefits and the option to withdraw without penalty will be reviewed with each potential participant. If the individual agrees, the CEERIAS Study Coordinator will contact them by their preferred method of communication and discuss the study in detail. We will also post IRB approved fliers at community sites including clinics, hospitals, and community centers such as churches with a number that interested participants may call. Community leaders/stakeholders will be recruited directly by CEERIAS research team members. We will solicit participation in the focus groups from partnering organizations and also an established list of known local groups and organizations.

To ensure effective recruitment and participation, we will contact interested participants at least 2 weeks prior to a scheduled focus group; send confirmation letters to selected participants 1 week before the focus group describing the time and location of the group, as well as any special instructions for participants, and a copy of the informed consent document to review in advance of the focus group; and make final reminder telephone calls to every participant 1 day before the group meets.

**Informed Consent:** Participants will be sent a copy of the consent document in advance of the focus group, but are not required to sign or bring it to the group. Research assistants will be available by phone to answer questions in advance. At the start of each focus group, the moderator and a research assistant will distribute the consent form and describe the focus group proceedings. Participants will be reminded of their right to quit at any time without penalty or to refuse to answer any questions, and we will review their privacy rights. There will be time for questions and concerns, including available research assistants and private space for those who request discussion. Once the informed consent document has been signed by each attendee, a signed copy will be provided to the participant for their records.

#### Key informant telephone interview (Aim 1)

We will also conduct key informant interviews of stakeholder/community leaders. We expect to successfully recruit 6-10 adults (age > 18 years) for layperson focus groups using a purposive strategy, recruiting subjects from each ethnic group in targeted neighborhoods. Since key informants will be generated from contacts with community organizations and advisory board members' input, we plan to recruit key informants using direct communications to individuals referred or recommended by our research team, CAB, and collaborating organizational partners.

**Informed consent:** Identified key informants will be asked to participate one-on-one by telephone using the focus group interview guide as a reference. Consent will be obtained by telephone at the start of the interview. Only those who agree to participate will continue with the interview. The interviews will be performed only in English.

#### **Stroke Promoter Training (Aim 2)**

Stroke Promoters will be identified by community organizations, Stroke Promoter referrals, and interested participants at community events when they complete the Participant Interest Form. The CEERIAS Study Coordinator or research assistant will obtain these forms, contact interested Stroke Promoters to provide an overview of the CEERIAS study, and confirm their interest in participation in an upcoming MIP-PACT training session. At training sessions, breakfast and lunch will be served. To ensure effective recruitment and participation, we will contact interested participants at least 2 weeks prior to a scheduled training session; send confirmation letters or emails to confirmed Stroke Promoters 1 week before the training data describing the time and location, and a copy of the informed

consent document to review in advance of the MIP-PACT training session; and make final reminder telephone calls to every participant 1 day before the training session.

Community participants attending the Stroke Promoter-led activities will be asked to fill out the Participant Interest Form and Participant Activity Evaluation Form. All persons who noted an interest (very interested or somewhat interest) in learning more about the CEERIAS study will receive a follow-up telephone call from the CEERIAS Study Coordinator to discuss the CEERIAS study, answer questions and review the informed consent. Enrollment into the Stroke Promoter Program or participation in the survey will follow the flowchart as noted in Figure 5. Each consenting individual will receive a unique study ID without personal identifiers. Demographic data from the Participant Interest Form and survey forms will be entered in a REDCap database stored within Northwestern University's firewalls and will be password protected. Access will be limited to approved study personnel only.

The participant may remove their data at any time by contacting either of the co-PIs. If consent is not obtained within 6 months from the date noted on the Participant Interest form, or if the patient refuses to participate after discussion of the study details, we will assess reasons for patient refusal to provide informed consent as this information will help us anticipate obstacles that will be encountered in the future. In addition, the CEERIAS study staff will destroy the Participant Interest Form and retain no participant data.

**Informed Consent:** The IRB approved informed consent form will be sent to the prospective Stroke Promoter participants in advance of the training session, but they will not be required to sign it or bring it to the group. This consent form will describe the overall goals of the CEERIAS study and the types of questions that will be asked of the Stroke Promoters. Information obtained will only be used for research purposes.

The CEERIAS Study Coordinator will be available by phone to answer questions in advance. At the start of each training session, the co-PIs and/or CEERIAS Study Coordinator will distribute the consent form and describe the training session agenda. Participants will be reminded of their right to quit at any time without penalty and we will review their privacy rights. There will be time for questions and concerns, including available research assistants and private space for those who request private discussion. Once the informed consent document has been signed by each attendee, a signed copy will be provided to each participant.

### **Aim 3 (Comparative Effectiveness-Knowledge and Attitudes)**

In year 2, community residents will be identified at hospitals, community organization sponsored stroke events (intervention and control groups), or recruited from persons indicating interest in the CEERIAS study. At non-intervention sites where educational events are being held, informed consents will be available for distribution and review to interested participants along with a copy of the Participant Interest Form to be completed at the site and returned to the contact person at each site. Incentives (\$25) will be provided to motivate individuals to participate.

**Informed Consent:** After submitting the Participant Interest Form, the participant will receive a follow-up telephone call to obtain verbal consent for the CEERIAS Study. In giving consent, the Study Coordinator will explain the CEERIAS study and review the consent form. After all questions and concerns have been addressed and the consenting has occurred, the Study Coordinator will begin the survey immediately if convenient or schedule a time to call back. If the patient refuses to participate after discussion of the study details, we will assess reasons for patient refusal to provide informed consent as this information will help us anticipate obstacles that will be encountered in the future. The CEERIAS study staff will destroy the Participant Interest Form and retain no participant

data. In addition, if consent is not obtained within 6 months from the date noted on the Participant Interest Form the form will also be destroyed.

**Risks:** Risks are very minimal and may include questions that will make participants uncomfortable. There is also an unlikely risk that personal information could be revealed. All subjects will be reassured about the risk of discomfort and we have taken careful precautions to ensure that the latter does not happen.

**Protection against Risk:** We will try to minimize participant discomfort with any questions or discussion by reassuring patients that they can skip any questions that they do not wish to answer. If this occurs, the research task will be stopped until the subject verbalizes readiness to continue, change the topic, or terminate the session. We will reassure participants also about security systems in place to prevent personal information being divulged. This is unlikely due to security settings at NU and stringent HIPAA and ethics training of all research staff.

**Potential Benefits:** There is no direct benefit to participation in the focus groups or survey data collection. However, some participants may feel satisfaction from the fact that their input may influence the community interventions we plan in Aim 2 of the study and community stakeholders and Stroke Promoters may feel good about contributing in a larger mission that serves their constituents.

**Alternatives:** The alternative is not to participate in this study. All individuals will be reassured that this will have no bearing on the care they receive or will receive for health-related concerns or participation in future studies.

